9.2.2 Objective Response Rate (ORR)

Objective Response Rate (ORR) per RECIST in Group A (main study population) is the primary endpoint of this study and is defined as the percent of patients with confirmed Complete Response (CR) or Partial Response (PR). ORR in Group B is an exploratory endpoint. ORR, along with the 95% exact confidence interval, will be estimated using the Clopper–Pearson method.

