9 STATISTICS

9.1 Statistical Methods

9.1.1 Statistical Design

This is a Phase 2 trial of the novel therapeutic sitravatinib in combination with pembrolizumab for the first-line treatment of patients with PD-L1 positive non-squamous metastatic NSCLC. The primary endpoint of this study is ORR as defined by RECIST 1.1, for patients treated with this combination. This study will enroll patients into two cohorts defined by PD-L1 status: PD-L1 TPS \geq 50% and TPS 1-49%. We will implement a Simon's Two-Stage Design to evaluate the efficacy of sitravatinib in combination with pembrolizumab for each cohort separately.

Each cohort will contain 35 patients, for a total of 70 patients (see discussion of sample size calculation below, section 9.1.3). Within each cohort, 30 patients will comprise the “main

study population" or Group A (see Study Schema 4.1), who will receive sitravatinib and pembrolizumab in combination starting on C1D1 of the study. It is hypothesized that this combination will result in at least 25% improvement in ORR when compared with historical control ORR of 39% for TPS \geq 50% and 17% in TPS 1-49%(6). Secondary endpoints include OS, PFS, Duration of Response (DOR) and Clinical Benefit Rate (CBR) in this population.

Initially patients will be randomized until five patients from each cohort have been assigned to Group B (to receive a 3-week run-in with pembrolizumab alone followed by the addition of sitravatinib on C2D1). The patients from this "pembrolizumab run-in" group, or Group B (see Study Schema 4.1), will not be included in the main statistical analysis of the primary endpoint. ORR, OS, PFS, DOR and CBR in Group B will be analyzed separately and will be secondary endpoints for this study.

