9.1.3 Sample Size Considerations

In Group A, for the cohort with TPS \geq 50%, we intend to enroll a maximum of 30 evaluable patients using Simon's minimax design. The sample size calculation is based on the desire to discriminate a promising ORR of 64% from a disappointing ORR of 39%(6). At stage 1, 17 subjects will be entered on the study. If \leq 7 responses are seen, the study will be terminated. At stage 2, 13 additional subjects will be entered. At the end of stage 2, if 16 or more subjects experience a response, the combination will be considered worthy of further study. *This design yields a type I error rate of 0.07 and power of 90% when the true response rate is 64%.*

In Group A, for the cohort with TPS 1-49%, we intend to enroll a maximum of 30 evaluable patients using the admissible two-stage design. The sample size calculation is based on the desire to discriminate a promising ORR of 42% from a disappointing ORR rate of 17%.(6) At stage 1, 16 subjects will be entered on the study. If ≤ 3 responses are seen, the study will be terminated. At stage 2, 14 additional subjects will be entered. At the end of stage 2, if 9 or more subjects experience a response, the combination will be considered worthy of further study. *This design yields a type I error rate of 0.05 and power of 91% when the true response rate is 42%.*

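### Minor: the Clopper-Pearson interval planned for Group A ORR is exact only for a fixed sample, so under the two-stage futility design its 95% coverage is not guaranteed; show a stagewise interval beside it

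*Combined protocol and SAP*

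**What the plan says.** Section 9.1.1 adopts a Simon "Two-Stage Design to evaluate the efficacy of sitravatinib in combination with pembrolizumab for each cohort separately". Section 9.1.3 gives the rules for Group A.

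- **TPS ≥50%:** 17 patients at stage 1; with 7 or fewer responses the rule is that once those "responses are seen, the study will be terminated". Otherwise "At stage 2, 13 additional subjects will be entered", and "if 16 or more subjects experience a response, the combination will be considered worthy of further study". The rates are 39% (disappointing) and 64% (promising), with stated type I error 0.07 and power 90%.
- **TPS 1-49%:** 16 patients at stage 1, stopping at 3 or fewer responses. Otherwise "At stage 2, 14 additional subjects will be entered", and "if 9 or more subjects experience a response, the combination will be considered worthy of further study". The rates are 17% and 42%, with stated type I error 0.05 and power 91%.

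Section 9.2.2 makes confirmed response in Group A the primary endpoint and plans one interval for it: "ORR, along with the 95% exact confidence interval, will be estimated using the" Clopper-Pearson method. It adds that "ORR in Group B is an exploratory endpoint". Section 9 contains no interval or estimate that takes the interim look into account.

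**The concern.** Clopper-Pearson inverts the binomial tails for a sample size fixed in advance. In Group A the sample size depends on the stage 1 result. A stage 1 stop yields an interval from 16 or 17 patients, and those stops add to the ways in which the upper limit can fall below the true rate. The 2.5% cap on that error is therefore lost. What is at stake is the accuracy of the label on the only interval planned for the primary endpoint, and the upper limit reported for a cohort that passes stage 1 and then falls short.

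**Working it through.** **Inputs** (section 9.1.3). TPS ≥50%: n1 = 17, stop if X1 ≤ 7, n = 30, success if total ≥ 16, p0 = 0.39, p1 = 0.64. TPS 1-49%: n1 = 16, stop if X1 ≤ 3, n = 30, success if total ≥ 9, p0 = 0.17, p1 = 0.42.

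**Step 1. Reproduce the plan's figures.** P(success | p) = Σ over x above the futility bound of P(X1 = x) × P(X2 ≥ cut-off − x), with X1 ~ Bin(n1, p) and X2 ~ Bin(30 − n1, p).

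| Cohort | Type I error | Power | Early stop at p0 / p1 | Reaches 30 and misses at p0 / p1 |
|---|---|---|---|---|
| TPS ≥50% | 0.0723 | 0.9006 | 67.2% / 4.6% | 25.5% / 5.3% |
| TPS 1-49% | 0.0499 | 0.9136 | 71.6% / 4.7% | 23.4% / 3.9% |

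The stated 0.07/90% and 0.05/91% are confirmed.

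**Step 2. Coverage of the planned interval.** Coverage(p) = Σ over all two-stage outcomes of P(outcome | p) × [p lies inside the Clopper-Pearson limits], using n = 17 or 16 for a stop and 30 otherwise.

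- At the design rates: 96.9% (39%), 96.1% (64%), 97.9% (17%), 96.9% (42%).
- Minimum over true ORR 10-80%: 94.4% near 68.7% (TPS ≥50%) and 94.2% near 45.9% (TPS 1-49%).
- Below 95% only for true ORR of about 68.7-69.3% and 45.9-47.2%.

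**Step 3. Where the shortfall comes from.** Take a true ORR just above the Clopper-Pearson upper limit for the total one short of the cut-off (15/30: 68.7%; 8/30: 45.9%).

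- TPS ≥50%, p = 0.6875. With a fixed 30 patients, P(X ≤ 15) = 2.47%, within the 2.5% allowance. Under the design, every stage 1 stop also misses (the upper limit at 7/17 is 67.1%): P(X1 ≤ 7) = 1.72%. Continuing and ending at 15 or fewer adds 1.68%. The total is 3.39% before rounding of the parts. The lower limit misses 2.17%, so coverage is 94.4%.
- TPS 1-49%, p = 0.459. With a fixed 30, P(X ≤ 8) = 2.49%. Under the design, P(X1 ≤ 3) = 2.39% and continuing to 8 or fewer is 1.62%, in total 4.00% before rounding of the parts. The lower limit misses 1.78%, so coverage is 94.2%.

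The lower-limit error never exceeds 2.5% in either cohort.

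**Step 4. A design-based comparison.** Rank stage 1 stops by count, then all 30-patient totals by count above them, and invert the exact two-stage tails at 2.5% per side. Minimum coverage over the same range is 95.2% and 95.1%, and neither tail exceeds 2.5%.

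| Result | Clopper-Pearson | Stagewise |
|---|---|---|
| TPS ≥50%, 12/30 | 22.7-59.4% | 25.7-67.2% |
| 13/30 | 25.5-62.6% | 27.4-67.5% |
| 15/30 | 31.3-68.7% | 32.0-69.9% |
| 16/30 (cut-off) | 34.3-71.7% | 34.7-72.1% |
| TPS 1-49%, 6/30 | 7.7-38.6% | 9.2-45.9% |
| 8/30 | 12.3-45.9% | 12.9-48.1% |
| 9/30 (cut-off) | 14.7-49.4% | 15.1-50.4% |

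Every stage 1 stop gives identical limits by both methods. From 18/30 and 12/30 upward they agree within 0.1 point.

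**The case against.** The defence is strong on size. Coverage exceeds 95% at every rate the design was built on, and the dips lie above the target rates in narrow bands. No decision uses the interval: section 9.1.3 decides on counts. Clopper-Pearson is commonly called the exact binomial interval, so the wording may only name a method, and prespecifying it as descriptive is legitimate. All of this stands and limits the point to a minor one. It does not make the interval exact for a sample whose size depends on the data.

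The stagewise interval also has a real weakness. Continuing outranks stopping, so its upper limit is nearly flat at low 30-patient totals: about 67% from 8 to 12/30 and about 46% from 4 to 6/30. At 8-13/30 it includes the 64% target, and at 4-6/30 the 42% target, where Clopper-Pearson excludes them. Those results have probability 14.0% at a true rate of 39% and 11.7% at 17%. This argues for showing both intervals, not for replacing one by the other.

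A reader might also infer that the raw ORR needs a bias-adjusted replacement. It is biased downward by 1.9 points at 39%, 1.6 at 17%, 0.5 at 64% and 0.6 at 42%, which is a conservative direction. The unbiased two-stage estimate (UMVUE) has larger root mean squared error at the null rates (0.1144 against 0.1015; 0.0907 against 0.0773) and lifts failing results, for example 49.4% against a raw 40.0% at 12/30. No need for it is shown.

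**Conclusion.** The point holds as a minor one. For Group A the 95% guarantee implied by the word exact fails by at most 0.6 points (TPS ≥50%) and 0.8 points (TPS 1-49%), entirely through an upper limit that is too low too often. Material differences arise only in a cohort that continues and misses its cut-off.

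Two stronger readings are not supported. One is that the planned interval overstates efficacy: its lower limit keeps the nominal error. The other is that the design or its conclusions are unsound: the stated type I error and power reproduce, and the counts decide.

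The figures assume exactly 17 or 16 patients analysed at stage 1 and 30 in total. Section 9.2.1 analyses all eligible patients, possibly without those never treated, so the attained numbers may differ. Another ordering of outcomes would give slightly different design-based limits. Group B has no futility look, so Clopper-Pearson is correct there.

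**What to change.** In section 9.2.2, for each Group A cohort:

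1. Keep the raw ORR with its Clopper-Pearson interval as the headline.
2. Report beside it a stagewise-ordered exact 95% interval, computed on the stage 1 and total numbers actually analysed.
3. State that the Clopper-Pearson interval ignores the interim look, that both intervals are descriptive, and that the response counts in section 9.1.3 decide.
4. Note that the stagewise upper limit is conservative and nearly flat at low 30-patient totals, so it can include the target rate in a failed cohort.

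Do not add a bias-adjusted estimate, and leave Group B on Clopper-Pearson alone. The cost is a few lines of code and a few sentences. Sample size, type I error, power and decision rules do not change. The price is a second interval that needs explaining when a cohort continues and does poorly.

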9.2.3 Overall Survival and Progression Free Survival Analysis

Overall Survival (OS) and Progression Free Survival (PFS) in the main study populations (ie groups 1A and 2A) are secondary endpoints for this study. OS and PFS in groups 1B and 2B are exploratory endpoints.

OS is defined as the time from date of treatment start to death due to any cause. PFS is defined as the time from first dose to first progressive disease (PD) or death due to any cause in the absence of documented PD. Survival status will be collected during initial and long-term follow-up as outlined in the Study Calendars (Section 6.1). If a patient discontinues treatment due to loss to follow-up or withdraws consent for use of data from medical records, surveillance of public sources of death information (e.g., published obituaries) should be undertaken and reported date of death recorded in the CRF. Patients with no event will be censored at the last available tumor assessment for PFS and at the last timepoint known alive for OS.

Kaplan-Meier estimates (product-limit estimates) will be presented for the analysis of PFS and OS together with a summary of associated statistics (median survival time, landmark survival rate estimates and estimates for every 6 months thereafter if applicable) including the corresponding two-sided 95% confidence intervals. The confidence intervals for the median will be calculated according to Brookmeyer and Crowley (1982) and confidence intervals for the survival function estimates at above defined time points will be derived using the log-log transformation according to Kalbfleisch and Prentice (1980). The estimate of the standard error will be computed using Greenwood's formula.

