Efficacy evaluations will be performed at 6 week intervals for the first 3 months, then 9 week intervals for the next 9 months and 12 week intervals thereafter. Efficacy evaluations will include CT scans of the chest/abdomen (and pelvis if indicated) and MRI brain if indicated (see Section 7.1.1) as well as survival assessments (see Section 7.1.2). Toxicity grading will occur as per CTCAE v5.0, with treatment interruptions or discontinuation of trial drugs as detailed in Sections 5.1.3 and 5.2.3. Treatment will continue for two years or until

progression of disease, unacceptable toxicity, patient refusal or death. Patients experiencing clinical benefit in the judgment of the Treating Investigator may continue study treatment beyond disease progression as detailed in Section 6.8. Post-treatment disease assessment will continue until objective disease progression or start of subsequent anti-cancer therapy, whichever is sooner.

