7.1 Efficacy Assessments

7.1.1 Radiographic Disease Assessment

All patients enrolled in the study are to undergo disease evaluations as outlined in the Study Calendars (Section 6.1). If symptoms develop or clinical deterioration occurs, patients may be imaged prior to the pre-specified time points for imaging. Patients discontinuing treatment prior to objective disease progression will be followed by radiographic evaluation until disease progression is documented or until the start of subsequent anti-cancer therapy, whichever is sooner.

Screening/baseline tumor assessments should include CT (with contrast, unless contraindicated) of the chest and abdomen (plus pelvis if indicated) and MRI of the brain

with and without gadolinium (preferred) or head CT with contrast if MRI is contraindicated. The allowable windows for screening/baseline assessments is 28 days prior to randomization.

Disease assessments performed on-study will include CT of the chest/abdomen (plus pelvis if indicated) and assessment of all known and suspected sites of disease. MRI brain should be performed on schedule with other radiologic disease evaluations if there is known CNS disease. If no known CNS metastases, MRI brain should be performed as clinically indicated. Assessments will be performed as per study calendars: every 6 weeks (starting from C1D1) for 3 months, every 9 weeks for 9 months and every 12 weeks thereafter. The allowable windows for on-study assessments is +/- 7 days. Assessments will be performed until objective disease progression is documented by the Investigator, or subsequent anti-cancer therapy is begun.

The Investigator's assessment of disease response and progression per RECIST 1.1 (for extracranial disease) and RANO-BM criteria (for intracranial disease) will be the basis for patient management and statistical analyses of radiology-based study endpoints. RECIST v1.1 and RANO-BM criteria are summarized in Appendices 3 and 4.

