9.2.4 Duration of Response

Duration of Response (DOR) for patients in Group A is a secondary endpoints for this study; DOR for Group B is an exploratory endpoint. DOR is defined as the time that measurement criteria are met for CR or PR (whichever is first recorded) until the first date that recurrent or progressive disease is objectively documented or to death due to any cause in the absence of documented PD.

The Kaplan-Meier method will be used for the subgroup of patients with a confirmed objective response in order to obtain the estimate of median DOR. Censoring for the DOR

endpoint will be assigned on the date of the last tumor assessment if no assessment of tumor progression is recorded and the patient does not die and prior to the start of subsequent anti-cancer therapy. Descriptive statistics will be provided for the DOR in responding patients (i.e., median duration of response and 95% CIs) by cohort, including the associated Kaplan-Meier curves.

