9.5 Handling of Missing Data

For all variables, only the observed data from patients will be used in the statistical analyses; there is no plan to estimate missing data. Patients without a valid clinical response assessment will be assigned a best overall response of not evaluable (NE). Data from patients who are lost to follow-up or have missing observations before reaching an endpoint in any of the time-to-event analyses will be treated as censored at the last available tumor assessment (or last time known alive).

10 Trial Administration

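### PFS has no rule for new anti-cancer therapy or missed scans: a late death is an event on its date, but a survivor is censored back at the last scan

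*Combined protocol and SAP*

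**What the plan says.** **Event and censoring (9.2.3).** PFS is the "time from first dose to first progressive disease (PD) or death due to any cause in the absence of documented PD". The censoring sentence reads "Patients with no event will be censored at the last available tumor assessment for PFS and at the last timepoint known alive for OS". Neither sentence mentions subsequent therapy or missed assessments.

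**When scans stop (4.2, 6.9.1, 7.1.1).** Section 7.1.1 states: "Assessments will be performed until objective disease progression is documented by the Investigator, or subsequent anti-cancer therapy is begun". Sections 4.2 and 6.9.1 agree.

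**When death collection stops (6.9.2, 7.1.2, 9.2.3).** Survival status is collected every 3 months until death or loss to follow-up. For patients lost to follow-up or withdrawing consent for record use, deaths are to be sought in public sources and recorded.

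**DOR (9.2.4).** DOR has the same death clause as PFS. Its censoring sentence applies where no progression is recorded and "the patient does not die and prior to the start of subsequent anti-cancer therapy".

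**Missing data (9.5).** The rule for incomplete cases is that those "lost to follow-up or have missing observations before reaching an endpoint in any of the time-to-event analyses will be treated as censored". The date used is that of the most recent scan, or the latest date of known survival.

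**The concern.** Once a patient starts new therapy without documented progression, progression is no longer looked for. From then on the only PFS event that can be recorded is death. If the patient dies, all the unscanned time up to death counts as progression-free. If the patient lives, none of the time after the last scan counts. Time at risk is thus set by the outcome, which Kaplan-Meier does not allow for.

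The result matches no clear estimand. It does not follow progression regardless of later therapy, because scans have stopped. It is not PFS before new therapy, because later deaths count. Death after a run of missed scans raises the same problem.

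PFS is a secondary efficacy endpoint in a trial without a comparator arm (4.4.4.1), so a shift caused by the counting rule could be read as drug effect. The situation is foreseeable: 6.9.1 plans follow-up for patients who stop treatment before progression, and 6.10 lists adverse events and global deterioration as reasons to stop.

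**Working it through.** **No plan figure to reproduce.** The documents give no PFS median, event count or power, and no rate of new therapy before progression. The check is a worked case, then a simulation.

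**1. One patient, two outcomes.** Last scan month 3, new therapy month 4, no progression documented.
- Dies at month 20: PFS event at 20 months under 9.2.3.
- Alive at the cut: PFS censored at 3 months.
- Censoring at the last scan before new therapy: 3 months in both cases.

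**2. Simulation inputs.**
- From the documents: scans every 6 weeks for 3 months, every 9 weeks for 9 months, then every 12 weeks (4.2); 24 months of recruitment and 24 of follow-up (4.3).
- Assumed: exponential PFS with median 6, 10 or 16 months; median survival after progression 6 to 30 months; 15% of PFS events are deaths without progression; 10-30% start new therapy before documented progression. The start is either driven by clinical progression not yet documented (informative) or unrelated to prognosis, such as for toxicity (non-informative).
- 200,000 patients per scenario; Kaplan-Meier under four rules.

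**3. Kaplan-Meier 12-month PFS at 48 months, 20% starting new therapy.** T = scans continue after new therapy; A = 9.2.3 as written; B = censor at last scan before new therapy; C = new therapy counted as an event.

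| Start of new therapy | Median PFS / post-progression survival (months) | T | A | A − T (points) | B | C |
|---|---|---|---|---|---|---|
| Informative | 6 / 12 | 0.274 | 0.344 | +7.0 | 0.334 | 0.269 |
| Informative | 10 / 12 | 0.459 | 0.515 | +5.6 | 0.519 | 0.454 |
| Informative | 16 / 6 | 0.615 | 0.645 | +3.0 | 0.665 | 0.611 |
| Non-informative | 6 / 12 | 0.275 | 0.296 | +2.1 | 0.274 | 0.220 |
| Non-informative | 10 / 12 | 0.460 | 0.473 | +1.3 | 0.459 | 0.367 |
| Non-informative | 16 / 6 | 0.612 | 0.617 | +0.5 | 0.611 | 0.490 |

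In the informative case the estimated median also moves, from 6.9 to 7.5-8.4 months or from 11.0 to 12.0-13.1 months. A separate simulation with about 14-22% switching gave +1.7 to +3.6 points (non-informative) and +5 to +7 points (informative).

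**4. Earlier cut.** At 30 months, 20% switching, non-informative, rule A is too low. At 12 months the gap is 0.4 to 0.9 points (for example 0.613 − 0.604 = 0.009). At 24 months it is 2 to 4 points (for example 0.374 − 0.334 = 0.040). Patients who go on to die stay in the risk set while comparable survivors have been removed at their last scan, so the deaths weigh too heavily. At 48 months with median 16 / 6, 24-month PFS is also slightly low: 0.382 − 0.368 = 0.014.

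**5. What the alternatives do.** B recovers T when switching is non-informative (0.459 against 0.460) but not when it is informative (0.519 against 0.459, no better than A at 0.515). C nearly recovers T when switching is informative (0.454 against 0.459) but falls well short when it is not (0.367 against 0.460).

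**6. Sections 9.2.3 and 9.5.** A patient is lost to follow-up before any PFS event, and a death is later found in public sources. Section 9.5 censors PFS at the last assessment; the definition in 9.2.3 makes the death an event. The two give different PFS values for one patient.

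**The case against.** **Materiality.** PFS is secondary and descriptive, with no test or threshold. With 30 Group A patients per cohort and 12-month PFS near 38%, the standard error is about √(0.38 × 0.62 / 30) = 0.089, or 9 points, which exceeds the bias. This stands as a limit on importance. However, the confidence interval reflects sampling error and does not allow for bias from the counting rule.

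**Direction.** A reader might infer that PFS is simply overstated. The documents do not support a fixed direction: they give neither the rate of nor the reasons for new therapy before progression, and the sign can reverse at an earlier cut or a later landmark.

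**DOR.** A reader might infer that a responder who switches is censored for DOR yet is a late PFS event. Section 9.2.4 does not establish this. It has the same death clause, and its censoring sentence requires that the patient does not die. Its reference to new therapy is unclear wording, and no contradiction with 9.2.3 is shown.

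**Section 9.5.** Scans that the protocol itself stops at new therapy are not plainly missing observations, so 9.5 does not clearly cover the switcher. For a patient who misses scans and then dies, the answer depends on how reaching an endpoint is read. The clear conflict is limited to the lost patient whose death is found later.

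**iPFS.** A reader might extend the late-death problem to iPFS. Section 9.2.8 defines it by intracranial progression only, with no death event, so the point does not carry over.

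**The remedy.** Censoring at new therapy does not restore the true value when switching follows clinical deterioration, which 6.10 makes plausible. This stands, and it is why a sensitivity analysis is needed as well.

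**Conclusion.** The gap holds. Section 9.2.3 lets the length of PFS follow-up depend on whether the patient dies, and it has no rule for new therapy or for death after missed assessments. At 48 months (the study length in 4.3), 12-month PFS is likely overstated by about 2 to 7 points if 15-20% start new therapy before documented progression. The bias is under 1 point where median PFS is long and switching is unrelated to prognosis. The switching rate, survival medians and reason for switching are all assumptions. At an earlier cut the bias can be downward. Sections 9.2.3 and 9.5 conflict for patients lost to follow-up whose deaths are found later, and 9.2.4 needs clearer wording. The primary ORR decision is untouched. This is an inexpensive correction worth making before the PFS analysis.

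**What to change.** - **9.2.3:** where there is no prior progression, censor PFS at the last evaluable tumor assessment on or before the start of subsequent anti-cancer therapy. Censor a death that follows two or more consecutive missed assessments at the last evaluable assessment.
- **Sensitivity analysis:** prespecify one that counts the start of new therapy as a PFS event. The censoring rule removes the bias only if switching is unrelated to prognosis; this analysis is close to right when switching follows clinical progression. Report both.
- **9.2.4:** reword the censoring sentence so that it says what happens at new therapy, including when the patient later dies, using the same rule.
- **9.5:** align to that rule, and say how a death found after loss to follow-up is handled for PFS.

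**Cost.** SAP wording and one more analysis. Subsequent therapies and their start are already recorded (6.9), so no new data are needed. A few late deaths no longer count as PFS events. Reported PFS will not necessarily fall: if switching is informative, the censoring rule gives a figure close to, or above, that of the present rule.
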